4.5.6 PHYSICIAN ASSESSMENTS

1. **Time to improvement of respiratory status.** This is defined as decreased or no need for oxygen supplementation to maintain optimal O₂ saturation (>94%)

2. **Measurement of the incidence of influenza complications**

We will record the incidence of following influenza complications associated with influenza after the start of study treatment: 1. Sinusitis; 2. Otitis Media; 3. Bronchitis; 4. Radiologically Confirmed Pneumonia, and 5. Hospitalization. At each study visit investigators will ask whether Sinusitis, Otitis Media, Bronchitis, Radiologically Confirmed Pneumonia and Hospitalization is present or not. If any of these is present, a specific report form shown below will be completed.

Form: Sinusitis

Did these symptoms start after the influenza treatment was given on Day 1?	Yes 	No 
Does the patient have a purulent nasal discharge?	Yes 	No 
Does the patient have facial pain, pressure sensation, or sensation of fullness?	Yes 	No 
Does the patient have nasal obstruction, congestion or stuffiness?	Yes 	No 
Have antibiotics been given to treat the sinusitis?	Yes 	No 

Form: Otitis Media

Did these symptoms start after the influenza treatment was given on Day 1?	Yes 	No 
Does the patient have pain or fullness in one or more ears?	Yes 	No 
Does the patient have tympanic membrane bulging or fullness on otoscopy?	Yes 	No 
Have antibiotics been given to treat the otitis media?	Yes 	No 

Form: Bronchitis

Did these symptoms start after the influenza treatment was given on Day 1?	Yes 	No 
Does the subject have a productive cough that has got worse after Day 1?	Yes 	No 
Has pneumonia been excluded?	Yes 	No 
Have antibiotics been given to treat the bronchitis?	Yes 	No 

Form: Pneumonia

Did these symptoms start after the influenza treatment was given on Day 1?	Yes 	No 
Does the patient have worsening cough since starting study treatment?	Yes 	No 
Does a Chest X Ray confirm pneumonia i.e. consolidation?	Yes 	No 
Have antibiotics been given to treat the pneumonia?	Yes 	No 

3. Hospital Recovery Scale

We will use the hospital recovery scale to assess participant's clinical status from day 1 to day 30. The hospital recovery scale provides 6 mutually exclusive conditions ordered from best to worst, and the score reflects the subject's worst situation on the day of assessment:

1. Not hospitalized
2. Non-ICU hospitalization, not requiring supplemental oxygen
3. Non-ICU hospitalization, requiring supplemental oxygen
4. Admitted to the ICU, not requiring invasive mechanical ventilation
5. Requiring invasive mechanical ventilation
6. Death

4.5.7 SELF ASSESSED MEASUREMENTS

1. TIME TO SYMPTOMS IMPROVEMENT

This is defined as time from the start of treatment to patient reported improvement in all seven influenza-associated symptoms for a duration of at least 24 hours. Symptoms that were present before the development of influenza symptoms will have to improve by at least one level. If patient was not experiencing any symptom, all symptoms will have to be rated as mild or absent. Patients will be given a diary to self-assess daily the severity of the following influenza-associated symptoms on a 4 points scale, at baseline and then for the first 15 days of the study.

	Date			
	No symptoms Score 0	Mild symptoms Score 1	Moderate symptoms Score 2	Severe symptoms Score 3
cough				
sore throat				
headache				
nasal congestion				
feverishness				
chills				
muscle or joint pain				

At baseline (i.e., the predose examinations), patients will be asked if preexisting symptoms existed (within the last 30 days) and if they were worsened by influenza. Patients will be asked to rate the severity at baseline that needs to improve. The modification for preexisting symptoms will be done as follows (ISON et al 2020, DOI:[https://doi.org/10.1016/S1473-3099\(20\)30004-9](https://doi.org/10.1016/S1473-3099(20)30004-9))

A. Symptoms that existed prior to developing influenza that are judged by the patient to be **worse at baseline** (before therapy) must improve from baseline severity

o Improvement in baseline severity is defined as follows:

Severe to moderate, mild, or absent

Moderate to mild or absent

Mild to mild or absent

Absent to mild or absent

B. Symptoms that existed prior to developing influenza that were judged by the patient to **NOT be worse at baseline** (before therapy) must have their baseline severity maintained

o Maintenance of baseline severity is as follows:

Severe is defined as severe or less than severe

Moderate is defined as moderate or less than moderate

Mild is defined as mild or absent

Absent is defined as mild or absent

- For **new symptoms at baseline** (before therapy), alleviation of symptoms assessment must be achieved

- o Alleviation of symptoms is defined as follows:

Severe is mild or absent

Moderate is mild or absent

Mild is mild or absent

Absent is mild or absent

Time to improvement of influenza symptoms is defined as the time from the initiation of the study treatment to the improvement of influenza symptoms for a duration of at least 24 hours. Once the patient's influenza symptoms will be alleviated, maintained, or improved (hereafter all will be called 'improvement') as defined above, the endpoint for that patient will be reached.

Patients who did not experience improvement of symptoms will be censored at the last observation time point.

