Participants will assess the severity of 7 influenza-associated symptoms (cough, sore throat, headache, nasal congestion, feverishness/chills, muscle/joint pain, and fatigue) on a 4-point scale (0 = no symptoms, 1= mild, 2 = moderate, and 3 = severe) as specified in section 4.5.7. Improvement is defined as: improvement pre-existing symptoms (i.e cough, fatigue, or muscle/join pain that existed prior to influenza) that were worse at baseline and improve at least 1 point from baseline; pre-existing symptoms not worse at baseline that maintain baseline severity; and new symptoms that are alleviated, defined as a symptom score of non (0) or mild (1).

Once all patient's influenza symptoms are alleviated, maintained, or improved (hereafter all will be called 'improvement') as defined above, the endpoint will be reached.

6. **Percentage of patients who experience each influenza-related complication** (hospitalization, death, sinusitis, otitis media, bronchitis, and radiologically-confirmed pneumonia) as an adverse event after the initiation of study treatment symptoms [symptoms [Time Frame: From Day 1 pre-treatment up to Day 30].
7. **Time to Return to Preinfluenza Health Status** [Time Frame: From Day 1 pre-treatment up to Day 30]. Participants will be asked to record their preinfluenza health status on a scale from 0 (worst possible health) to 10 (normal health [for someone same age and condition]), and their health status at baseline and every day after initiation of study treatment on the same scale as specified in section 4.5.7. Return to preinfluenza health status is defined as time from the initiation of the study treatment to the first time when the health status score was equal to or higher than the preinfluenza health status score.
8. **Time to viral clearance**, as assessed by difference in Percentage of Participants Positive by Influenza plaque assay and qPCR at each time-point (in each treatment group) The definition of the time to sustained cessation of infectious virus detection is the time

between the start of treatment and when virus titer remained below the detection limit on all subsequent sampling time points.

9. Measure treatment-emergent variants of neuraminidase and polymerase known to confer antiviral resistance to oseltamivir in each arm by direct next-generation sequencing symptoms [Time Frame: From Day 1 pre-treatment up to Day 30]

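### Secondary endpoint 5 (time to improvement of influenza symptoms) is inconsistently specified: one sentence of 4.5.7 demands improvement where the scoring rules accept maintenance, and the diary grid as printed has no fatigue row

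*Combined protocol and SAP*

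**What the plan says.** Secondary endpoint 5 in section 2.1 refers to section 4.5.7 for its scale. Section 4.5.7 starts from "improvement in all seven influenza-associated symptoms for a duration of at least 24 hours". Its second sentence reads: "Symptoms that were present before the development of influenza symptoms will have to improve by at least one level".

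Later in the same section a three-part scheme is introduced with "The modification for preexisting symptoms will be done as follows":

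- Rule A: pre-existing symptoms that were worse at baseline must improve.
- Rule B: pre-existing symptoms that were not worse at baseline "must have their baseline severity maintained".
- New symptoms must fall to mild or absent.

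Section 2.1 agrees with Rule B, since it counts "pre-existing symptoms not worse at baseline that maintain baseline severity" as improvement. Section 4.5.7 closes by saying that once symptoms are alleviated, maintained or improved, "the endpoint for that patient will be reached". On censoring it says: "Patients who did not experience improvement of symptoms will be censored at the last observation time point".

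Section 2.1 lists the seven symptoms as "cough, sore throat, headache, nasal congestion, feverishness/chills, muscle/joint pain, and fatigue". The inclusion criteria (4.1.1) and Appendix 1 note o give the same seven, and note o has patients record them in the diary. The 4.5.7 grid as printed has rows for cough, sore throat, headache, nasal congestion, feverishness, chills, and muscle or joint pain.

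The time frame in section 2.1 runs to Day 30. Section 4.5.7 and note o both stop symptom entries at day 15. Section 4.5.7 asks for daily entries; note o asks for two a day through day 9 and one a day after that. The self-assessment row of Appendix 1 also carries a mark at D30.

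**The concern.** Every one of the seven symptoms has to qualify, so a single symptom can decide whether a patient has an event. Take a patient whose long-standing cough was not made worse by influenza and stays at the same score while all else resolves. Under Rule B that patient reaches the endpoint. Under the second sentence the patient does not, and is censored. Such patients are expected: section 2.1 itself names cough, fatigue and muscle or joint pain as symptoms that may predate influenza.

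The diary matters for the same reason. If the printed grid is the one patients fill in, a required component of the endpoint is not collected on it. The daily calls in section 3.1 do not clearly fill the gap: they cover only the first 10 days and no symptom list is given for them.

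What is at stake is whether two analysts working from this protocol would derive the same event times for the Kaplan-Meier estimates planned in the Statistical Considerations.

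**Working it through.** The plan states no figure on this point, so the check is to code each rule and compare.

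**Scoring rules.** Scores from 4.5.7: absent 0, mild 1, moderate 2, severe 3. Let b be the baseline score of a symptom that is present (1 to 3) and l a later score (0 to 3). That gives 3 × 4 = 12 transitions.

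| Rule | Condition | Mild | Moderate | Severe | Qualify |
|---|---|---|---|---|---|
| 4.5.7, second sentence | b − l ≥ 1 | 1 | 2 | 3 | 6 |
| 4.5.7, Rule B | l ≤ b | 2 | 3 | 4 | 9 |
| 4.5.7, Rule A | severe: l ≤ 2; moderate or mild: l ≤ 1 | 2 | 2 | 3 | 7 |
| 2.1, worse at baseline | b − l ≥ 1 | 1 | 2 | 3 | 6 |

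- Second sentence against Rule B: 9 − 6 = 3 of 12 transitions conflict. They are mild-mild, moderate-moderate and severe-severe, that is, every unchanged symptom.
- Rule A against section 2.1: 7 − 6 = 1 of 12 conflicts, namely mild-mild.

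Baseline scores of absent are left out because such a symptom has no level to lose. If they are kept, there are 16 transitions and the first conflict grows to 5 (adding absent-absent and absent-mild). These counts show where the rules differ; they do not estimate how many patients are affected.

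**Diary rows.** The printed grid has 7 rows. Feverishness and chills take two rows for one defined item, so the grid covers 7 − 1 = 6 defined symptoms. The one without a row is fatigue. The count of seven therefore matches, but the content does not.

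**Time frame.** Days in the endpoint time frame: 30. Days with scheduled symptom entries: 15. Days without: 30 − 15 = 15. An improvement that first occurs on days 16 to 30 lies inside the time frame but cannot be dated from daily entries.

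**The case against.** The best reply on the main conflict is that the text already settles it. The three-part scheme is presented as the modification for pre-existing symptoms, the closing text of 4.5.7 counts maintained symptoms toward the endpoint, and section 2.1 repeats this. Under the second sentence alone, maintenance would have no role. This stands: a reader might infer that the protocol leaves two rival definitions with nothing to choose between them, and the documents do not support that. What remains is a sentence that contradicts the evident rule and that no text sets aside.

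On the diary, a reader might infer that the trial does not collect fatigue. The documents do not support that either. Note o assigns all seven symptoms, fatigue included, to the patient diary, so the conflict is between the 4.5.7 grid and note o with section 2.1. The grid was also read from extracted PDF text, in which tables can break: a wrapped label for feverishness or chills together with a lost fatigue row would restore exactly the seven intended symptoms. Against that, the grid shows seven rows and the label for muscle or joint pain is intact, so a lost row is not established.

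On the time frame, a reader might infer that everyone who first improves on days 16 to 30 is censored. That is too firm. The D30 self-assessment mark could mean that symptoms are scored then, or it could serve the daily health-status scale in 4.5.7; note o, attached to that row, describes only symptoms and only to day 15.

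Finally, the mild-to-mild case under Rule A is narrow, and daily against twice-daily may be general text against schedule detail. Both are fair, and both are ranked here as editorial.

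**Conclusion.** The endpoint should be corrected before its event times are derived.

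- **Improvement against maintenance.** High confidence. The second sentence of 4.5.7 disagrees with Rule B, section 2.1 and the closing text of 4.5.7 on every unchanged symptom (3 of 12 transitions). Followed literally, it would censor patients with a stable chronic symptom.
- **Fatigue row.** Moderate confidence, pending a look at the original page and the diary in use. As printed, the grid covers 6 of 7 symptoms and conflicts with section 2.1 and note o.
- **Lesser points.** Rule A's mild-to-mild, the Day 30 time frame against a 15-day diary, and the entry frequency need reconciling. An improvement first occurring on days 16 to 30 may be censored or dated only at D30; the text does not say which.

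The reach is limited. The endpoint is secondary, and the Statistical Considerations call all between-arm comparisons exploratory. The primary viral-load analysis and the sample size are unaffected. The number of patients affected cannot be computed, because the documents give no frequency of pre-existing symptoms or of late improvement.

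**What to change.** 1. Delete the second sentence of the 4.5.7 definition, or limit it to pre-existing symptoms that were worse at baseline. If it is limited, settle Rule A's mild row in the same edit, since the one-level requirement would still conflict with mild-to-mild. State the same rule in 2.1 and 4.5.7.
2. Check the grid in the original PDF and the diary in use. If fatigue is absent, make the grid match section 2.1 and note o (fatigue included, feverishness/chills as one item), and report any patients enrolled without fatigue scores.
3. Align the endpoint time frame, the censoring day and the diary length, and say which self-assessed measure the D30 mark covers.
4. State one diary frequency.

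The cost is protocol wording and at most one diary page. Setting the horizon at day 15 censors later improvers by design; keeping day 30 means a longer symptom diary and more patient burden. Fatigue scores that were never collected cannot be recovered, so the diary check should come first.

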1. BACKGROUND

1.1 BACKGROUND ON INFLUENZA

Influenza is an acute respiratory infectious disease caused by a virus of the orthomyxovirus family. Two forms are known to infect humans, influenza A and B. These viruses cause an acute febrile infection of the respiratory tract after an incubation period of 1 to 4 days, characterized by the sudden onset of fever, cough, fatigue, headache, and myalgia. Annual influenza epidemics are thought to result in between 3 and 5 million cases of severe illness, and between 250,000 and 500,000 deaths every year around the world (WHO 2017).

Although the condition is usually self-limiting in healthy adults, it can be associated with substantial morbidity and occasional mortality in children, the elderly, and the immunocompromised (Paules and Subbarao 2017). Hospitalization due to severe influenza is associated with high mortality (4%–8%), intensive care unit (ICU) admission (5%–17%), and prolonged hospital stays of between 5 and 9 days. During a pandemic season, the outcomes may be more serious, with up to 34% of patients requiring ICU care and a mortality rate as high as 15% (Lee and Ison 2012).

The influenza viruses have a segmented, negative-sense, single-stranded, lipid-encapsulated RNA genome; they range between 80 and 100 nm in size. Subtypes are defined according to glycoproteins present in the viral lipid coat. The hemagglutinin complex (HA) is the major surface protein of the virus. The neuraminidase (NA) proteins are the second major surface proteins in the virion and play a role in enhancing virus penetration of the mucus layer around the target cell and in release of virus from the cell surface. The matrix-2 (M2) protein triggers the disintegration of the virion during virus entry into the cell and may also be involved in protecting the HA prior to assembly of new virus particles.

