In the Flagstone study, the incidence of adverse events was comparable between the two treatment arms regardless of the number of Xofluza or placebo doses that were received. One serious adverse event (orthostatic hypotension) in the placebo arm was considered treatment related.

Table 4: FLAGSTONE – Incidence of Adverse Events*

	Baloxavir + SoC NAI (n=239)	Placebo + SoC NAI (n=124)	All Patients (n=363)
Patients with ≥ 1 AE	108 (45.2%)	62 (50.0%)	170 (46.8%)
Total number of AEs	279	180	459
Deaths	4 (1.7%)	7 (5.6%)	11 (3.0%)
Patients withdrawn from treatment due to AE	3 (1.3%)	4 (3.2%)	7 (1.9%)
Serious AEs, patients (%)	29 (12.1%)	19 (15.3%)	48 (13.2%)
Treatment-related serious AEs, patients (%)	0	1 (0.8%)	1 (0.3%)
Treatment-related AEs, patients (%)	8 (3.3%)	8 (6.5%)	16 (4.4%)

Notes: *Safety population. Investigator text for AEs encoded using the MedDRA version 23.0. Related AEs are related to study drug only.

Abbreviations: AE(s)=adverse event(s); MedDRA=Medical Dictionary for Regulatory Activities; NAI=neuraminidase inhibitor; SoC=standard of care

Our study will randomize SCT recipients with influenza to receive baloxavir + oseltamivir (SOC) or oseltamivir + baloxavir matching placebo and assess if the combination of baloxavir with oseltamivir will translate in a more rapid decrease of viral load and faster symptoms resolutions when compared to oseltamivir alone. It will also test if combination therapy may lower the incidence of drug-resistant influenza variants.

In summary, there is a strong rationale and a positive benefit-risk assessment for studying Xofluza combination therapy in SCT recipients. Safety and efficacy results suggest that Xofluza has an acceptable clinical safety profile and could benefit in immunocompromised patients. Given the poor treatment responses to single therapy in SCT, this population is considered appropriate for trials of combination therapy. The benefit-risk ratio for Xofluza in combination with oseltamivir is expected to be acceptable in this setting.

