For secondary viral loads related endpoints, summary statistics in terms of mean, standard deviation, median and range will be calculated for each arm at each time points among patients with relevant measurements. Longitudinal analyses using mixed effects repeated measures will be used to model the mean viral loads overall time. Contrasts of interest including between arm differences will be explored using simultaneous tests of general linear hypotheses. If normality is a concern, log-transformed and standardized viral load data will be used. Longitudinal analysis will be carried out among patients with at least one relevant viral load measurement. Kaplan-Meier estimates will be generated for time to events endpoints such as time to Improvement of Individual Influenza Symptoms, the time to viral clearance and time to return to preinfluenza health status for each study arm. Between study arm difference in these endpoints will be explored using the generalized Wilcoxon test.

Categorical data such as the occurrence of treatment-emergent variants of neuraminidase and polymerase by direct next-generation sequencing and AE's will be summarized in terms of counts and proportions separately for each arm.

Between arm difference in the categorical variable will be explored using Fisher's exact test. The study is likely will not have adequate power to detect between arm differences and all the between arms comparisons are considered exploratory. Summary statistics generated for study endpoints for each arm will provide useful information for planning future studies.

The power calculations were performed using PASS 15 Power Analysis and Sample Size Software (2017). NCSS, LLC. Kaysville, Utah, USA, ncss.com/software/pass. All comparisons will be two-tailed, with a significance level at 0.05 and 95% confidence intervals will also be reported. All analyses will be performed in SAS Version 9.4 (2019), SAS Institute, Inc., Cary, NC; and R Version 4.0.4 (2021).

Note: The statistical considerations section was written by [name], MS, and revised by [name], in the Division of Biostatistics, Department of Population Health Sciences, Weill Cornell Medicine.

Influenza sequence analysis will be performed by [name], Director of Systems Genomics Section at the Laboratory of Parasitic Diseases of NIAID/NIH and expert in Influenza evolution.

No interim analysis is planned for this study

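### Patients who die before improving are censored at their last observation, so the Kaplan-Meier share improved is overstated and such deaths carry no penalty in the symptom endpoint

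*Combined protocol and SAP*

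**What the plan says.** Section 4.5.7 gives one censoring rule for time to symptom improvement: "Patients who did not experience improvement of symptoms will be censored at the last observation time point". It does not mention death and makes no exception for it. Statistical Considerations specifies the estimator, "Kaplan-Meier estimates will be generated for time to events endpoints such as time to Improvement of Individual Influenza Symptoms", and extends it to time to viral clearance and return to preinfluenza health. For the comparison it says: "Between study arm difference in these endpoints will be explored using the generalized Wilcoxon test". It names no competing-event method, composite, worst-rank rule or sensitivity analysis for death.

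Death is counted elsewhere. Secondary endpoint 6 in section 2.1 lists it among the complications ("hospitalization, death, sinusitis, otitis media, bronchitis, and radiologically-confirmed pneumonia"), and it is the worst category of the hospital recovery scale in section 4.5.6. Neither is linked to time to improvement. For viral clearance and return to preinfluenza health, no censoring rule of any kind is given.

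The observation window is also unsettled. Section 2.1 gives the symptom endpoint a time frame to day 30. Section 4.5.7 has the diary kept "at baseline and then for the first 15 days of the study", and note o of Appendix 1 likewise stops at day 15.

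**The concern.** Reading one minus the Kaplan-Meier curve as the share improved assumes that a censored patient would have gone on to improve like those still at risk. That is reasonable for someone who stops filling in a diary. It cannot hold for someone who has died. Censoring at death shrinks the denominator at every later improvement, so the curve rises faster than the true proportion of randomised patients who improve.

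What is at stake is mainly the per-arm description. Statistical Considerations says the arm-level summaries are meant to inform later studies, and these curves are among them. The comparison is also affected, because an arm loses nothing on this endpoint for deaths before improvement. If deaths followed the pattern in Table 4 of section 1.3, with more on placebo, the rule would lean towards the control arm.

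**Working it through.** **The plan's own figures.** None depends on this rule. The plan's 80% power statements concern viral load. The within-arm one reproduces (n = 15, difference 2.33, SD 3 taken as the SD of the differences: power 0.799). No power, event count or death rate is given for time to improvement.

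**Inputs from the documents.** 15 patients per arm (section 3.1 and Statistical Considerations). Deaths in the prior hospitalised-patient trial: 4/239 = 1.7% with the combination and 7/124 = 5.6% with placebo (section 1.3, Table 4). The documents give no improvement-time distribution and no times of death, so those below are assumptions.

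**1. How many deaths to expect, of any timing**
- Expected per arm: 15 × 4/239 = 0.25; 15 × 7/124 = 0.85.
- At least one in the combination arm: 1 − (1 − 4/239)^15 = 22%.
- At least one in the control arm: 1 − (1 − 7/124)^15 = 58%.
- At least one in the trial: 1 − (1 − 4/239)^15 × (1 − 7/124)^15 = 67.5%.
- Two or more in an arm: 2.5% (combination) and 21% (control). Three or more: 0.2% and 4.9%.

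**2. How many precede improvement.** Only these are mishandled. Assume exponential improvement with median 5 days, and deaths uniform on days 3 to 10 and independent of improvement. The share of deaths that come first is

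(1/7) ∫ from 3 to 10 of 2^(−t/5) dt = (1/7)(5/ln 2)(2^−0.6 − 2^−2) = 0.42.

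The chance of at least one such death in the trial is then 1 − (1 − 0.42 × 4/239)^15 × (1 − 0.42 × 7/124)^15 = 37%. If deaths fall mainly among patients who are not improving, the figure lies between 37% and 67.5%.

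**3. Shift in the day-15 share improved.** Simulation of 4,000 arms of 15 under the same assumed times. Each cell gives the share with deaths counted as not improved, then the share under the written rule.

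| Deaths in arm | All deaths precede improvement | Deaths independent of improvement |
|---|---|---|
| 1 | 82% → 86% | 86% → 88% |
| 2 | 76% → 85% | 84% → 88% |
| 3 | 70% → 83% | about 81–82% → 87–88% |

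Check on the first cell: (14/15) × (1 − 2^(−15/5)) = 0.933 × 0.875 = 0.817. With all deaths preceding improvement, one death shifts the estimate by 5 points at an assumed median of 4 days and by 3 points at 8 days. Across these cases one death is worth about 2 to 5 points.

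**4. Effect on the comparison.** With equal improvement hazards while alive (assumed median 6 days), 3,000 simulated trials at 1.7% versus 5.6% dying before improvement gave a mean Gehan Z of 0.01 under the written rule. With deaths kept as non-improvers it was 0.09. The rejection rate was 5.1% either way. At an assumed 0% versus 20%, the mean Z was −0.03 and 0.39.

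**5. A constructed case where the order reverses.** Give both arms the same 12 improvers, evenly spaced over days 3 to 14. In arm A the other three are alive and unimproved at day 15. In arm B the other three die on day 2. The written rule gives 80% versus 100% improved by day 15 and medians of 10 versus 8 days, favouring the arm with three deaths (Z = 0.88, p = 0.38). With deaths kept in the risk set, both arms are at 80% with a median of 10 days and Z = 0.

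**The case against.** The strongest reply has four parts.

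- **The curve can be defended as a different quantity.** Censoring at death targets the rate of improvement while alive, which is a recognised cause-specific quantity. This stands as far as it goes: the error is in reading the complement of the curve as the share improved. But the plan names no such target, and a per-arm Kaplan-Meier curve of time to improvement will be read as that share.
- **Deaths are not hidden.** They are reported by arm in secondary endpoint 6 and in the hospital recovery scale. This also stands. It does not correct the improvement curve.
- **The death rates are borrowed.** They come from hospitalised patients. This trial enrols outpatients and inpatients (section 3.3.1). It also admits chemotherapy and CAR-T patients, with a minimum of only 10 allogeneic recipients (section 4.1.1). The statement in section 1.3 about increased death in transplant recipients therefore does not cover the whole cohort. No document gives a death rate for it.
- **The endpoint carries little weight.** It is secondary, and the plan itself calls all between-arm comparisons exploratory and likely underpowered.

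A reader might infer that the arm with more deaths will come out ahead, or that the rule would conceal a benefit of baloxavir. The documents do not support either as a general result. When deaths are unrelated to improvement, the rule makes the arms look alike. It makes the arm with more deaths look strictly better only if those who die would not have improved. At the cited rates the mean Z moves by about 0.08.

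**Conclusion.** The rule as written mishandles deaths before improvement and biases the estimated share improved upwards. The direction follows from the estimator and needs no outside source. The size is modest: 0 to 1 death per arm expected, about 2 to 5 percentage points per death in the day-15 estimate, and rarely a different test result. The chance that the rule matters at all is about 37% if deaths are independent of improvement. The figure of about 68% is for a death at any time and should not be read as the chance of bias. The two- and three-death rows show the mechanism but are unlikely at the cited rates.

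These figures rest on borrowed death rates and on assumed improvement and death times. The viral-load co-primaries and the sample size are unaffected. The point deserves a correction because that is nearly free, and because choosing a rule after unblinding, with one or two patients at issue, would be hard to defend.

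**What to change.** In section 4.5.7 and Statistical Considerations, add wording such as: *A patient who dies before meeting the endpoint is counted as not having met it and stays in the risk set, censored at the last day of that endpoint's observation window. A living patient lost to follow-up is censored at the last observation.* Reporting cumulative incidence of improvement with death as a competing event, with Gray's test, is an acceptable alternative. The two give the same curve when there is no other early censoring.

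State the same rule for time to viral clearance and time to return to preinfluenza health, and give each of them a censoring rule and a window.

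In the same edit, reconcile the symptom window: the day-15 diary in section 4.5.7 and Appendix 1 note o against day 30 in section 2.1. Deceased patients and living non-improvers must be censored on the same day. If the dead were carried to day 30 while living non-improvers stopped at day 15, the dead would stay at risk longer than the living.

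The cost is a few sentences, settled before unblinding. No new data, visits or patients are needed.
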